### **Subgroup Analysis**

Subgroup analyses will be conducted comparing ORR between the treatment arms in each stratum used in the randomisation. If there are sufficient patients in each stratum, a logistic regression comparing treatments may be used to compare treatments. The results of the analysis will be presented in terms of an odds ratio in analogy with the primary logistic regression described above. If there are not enough responses for meaningful subgroup analysis using logistic regression, then a CMH test may be used instead. Objective response rate within each stratum will be presented with a two-sided 95% CI using the Clopper-Pearson method.

The odds ratios and associated two-sided 95% profile likelihood CIs will be summarised and presented on a forest plot, along with the results of the overall primary analysis.

No adjustment to the significance level for testing of subgroups will be made since the subgroup analyses **CCI** may only be supportive of the primary analysis of ORR.

#### **9.4.2.2 Analysis of Secondary Efficacy Endpoints**

##### **Progression-free Survival**

Progression-free survival is defined as the time from randomisation until the date of objective disease progression per RECIST 1.1 as assessed by the investigator or death due to any cause regardless of whether the patient withdraws from therapy or receives another anti-cancer therapy prior to progression. Patients who have not progressed or died at the time of analysis will be censored at the time of the latest date of assessment from their last evaluable RECIST assessment.

However, if the patient progresses or dies after 2 or more missed visits, the patient will be censored at the time of the latest evaluable RECIST assessment. If the patient has no evaluable visits or does not have baseline data they will be censored at Day 1 unless they die within 2 visits of baseline: in such a case, the death date will be used as the event date.

The PFS time will always be derived based on scan/assessment dates, not visit dates.

The RECIST assessments/scans contributing towards a particular visit may be performed on different dates. The following rules will be applied:

- Date of progression will be determined based on the earliest of the dates of the component that triggered the progression.
- When censoring a patient for PFS, the patient will be censored at the latest of the dates contributing to a particular overall visit assessment.

Prior to CSP V3.0, the primary analysis of PFS was to occur 6 months after the last patient was randomised. A final analysis was to occur after the earlier of 18 months after the last patient was randomised or when 70% of patients had progressed or died. Under CSP V3.0, as a result of AstraZeneca's decision to terminate study recruitment early, there will be no primary analysis at the originally planned timepoint. Following early termination of study recruitment, an initial DCO will occur to allow an early review of data by AstraZeneca. The study will be unblinded after completion of data cleaning activities on this initial DCO data, and patients on savolitinib monotherapy (savolitinib plus placebo) will be given the opportunity to cross-over to the savolitinib plus osimertinib arm. If the investigator believes patients are gaining clinical benefit and patients have not reported PD, patients may continue to receive savolitinib monotherapy. All patients will be followed until the final analysis. A final DCO will occur 9 months after the last patient has been randomised, after which the final analysis will be performed. CCI

Progression-free survival based on investigator assessment will be analysed using a stratified log-rank test adjusting for the same factors as for ORR for generation of the p-value. The effect of treatment will be estimated by the HR together with its corresponding 95% CI for the FAS. An HR less than 1 will favour savolitinib plus osimertinib. The HR and its CI will be estimated from a stratified Cox Proportional Hazards model (with ties = Efron and baseline stratification) and the CI calculated using a profile likelihood approach. If there are insufficient events per strata, a log-rank test will be used to analyse PFS instead of a stratified log-rank test.

Kaplan-Meier plots of PFS will be presented by treatment arm. Summaries of the number and percentage of patients experiencing a PFS event, and the type of event (RECIST 1.1 or death) will be provided along with summaries of PFS (n, events, medians, quartiles, proportion progression free at 3, 6, 9, and 12 months and corresponding 95% CIs) by treatment group.

The assumption of proportionality will be assessed. Proportional hazards will be tested firstly by examining plots of complementary log-log (event times) versus log (time) and, if these raise concerns, by fitting a time dependent covariate (adding a treatment-by-time or treatment-by-ln[time] interaction term) to assess the extent to which this represents random variation. If a lack of proportionality is evident, the variation in treatment effect can be described by presenting piecewise HR calculated over distinct time-periods for example 0 to 6 months, 6 to 12 months etc. In such circumstances, the HR from the primary analysis can still be meaningfully interpreted as an average HR over time unless there is extensive crossing of the survival curves. If lack of proportionality is found this may be a result of a treatment-by-covariate interaction, which will be investigated.

The treatment status at progression of patients at the time of analysis will be summarised. This will include the number (%) of patients study intervention prior to progression, the number

(%) of patients who have not progressed and were on treatment or discontinued treatment. This will also provide distribution of number of days prior to progression for the patients who have discontinued treatment.

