**Table 1 Schedule of Activities for Randomised Treatment**

Visit	Pre-screening	Screening	Intervention Period				Follow-up a			Details in CSP Section or Appendix			
			Cycle 1 (28-day cycle)				Cycles 2 to 6 (28-day cycle)	Cycle 7 onwards (28-day cycle)	Treatment discontinuation visit		28-Day follow-up visit b	Survival follow-up visit	
Week (Day 1 of)	NA	-4 to 0	1 to 4				5 to 24	25 onwards		Within 7 days of the final dose of study intervention			± 7 days
Study day		-28 to -1	1 to 28				29 to 168	169 onwards					
Day of cycle			1	8	15	22	1	1					
Visit window			± 1 day				± 3 days	± 3 days					
PK measurements													
Blood sample for PK analysis of savolitinib m, n			X n				Day 1 of Cycles 2, 3, and 6 n					8.5.1	
Blood sample for PK analysis of osimertinib m, n			X n				Day 1 of Cycles 2, 3, and 6 n					8.5.1	
Efficacy measurements													
Tumour imaging o (RECIST 1.1)		X p	Q6W (± 7 days) up to 24 weeks relative to randomisation, then Q8W (± 7 days) until objective disease progression									8.1	
Study intervention administration													
Dose with osimertinib or placebo			X (daily dosing)										6.1
Dose with savolitinib			X (daily dosing)										6.1

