### 9.4 Statistical Analyses

Under CSP V3.0, the SAP will be finalised prior to the unblinding of the study that is to occur following early study recruitment termination, for the purpose of an early review of the study data by AstraZeneca.

The SAP will include a more technical and detailed description of the statistical analyses described in this section. This section is a summary of the planned statistical analyses of the most important endpoints including primary and key secondary endpoints.

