#### **9.4.2 Efficacy**

##### **Investigator RECIST Based Assessments**

From the investigators review of the imaging scans, the RECIST tumour response data will be used to determine each patient's visit response according to RECIST 1.1. It will be used to determine the endpoints of ORR, PFS, DoR and tumour size change.

At each tumour assessment, patients will be programmatically assigned a RECIST 1.1 visit response of CR, PR, SD or PD depending on the status of their disease compared with baseline and previous assessments. If a patient has had a tumour assessment which cannot be evaluated, the patient will be assigned a visit response of NE (unless there is evidence of progression in which case the response will be assigned as PD).

Investigator-assessment of PD per RECIST 1.1 of patients receiving savolitinib plus placebo is required prior to cross-over to savolitinib plus osimertinib.

Please refer to [Appendix H](#) for the definitions of CR, PR, SD, PD and NE.

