### **Duration of Response**

The DoR is defined as the time from the date of first documented response until date of documented progression or death in the absence of PD (ie, date of PFS event or censoring – date of first response + 1). The end of response should coincide with the date of progression or death from any cause used for the PFS endpoint. The time of the initial response will be defined as the latest of the dates contributing towards the first visit response of CR or PR.

If a patient does not progress following a response, then their DoR will use the respective PFS censoring time.

If there are sufficient numbers of responders, and sufficient numbers of responses that have progressed by the point of the analysis, Kaplan-Meier plots of DoR in the responding patient will be produced and appropriate descriptive summary statistics will be presented (n, number of responses that have progressed, median, quartile, minimum and maximum DoR) by treatment group without any formal comparison or p-value attached.

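### The PFS rule for progression after two or more missed visits, as worded, censors at the progression scan itself and credits the unobserved gap as event-free time

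*Supplement*

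**What the plan says.** All references are to the current protocol (CSP V3.0); no SAP is shown.

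- **Patients without an event** (9.4.2.2, Progression-free Survival). They are "censored at the time of the latest date of assessment from their last evaluable RECIST assessment", meaning the last such assessment on record.
- **The missed-visit exception** (same place). It reads: "the patient progresses or dies after 2 or more missed visits, the patient will be censored at the time of the latest evaluable RECIST assessment". Nothing limits the assessment to those before the missed visits.
- **What is evaluable** (9.4.2, Investigator RECIST Based Assessments). The rule for NE is: "If a patient has had a tumour assessment which cannot be evaluated, the patient will be assigned a visit response of NE". A scan that shows progression is carved out of it by a bracketed exception: "unless there is evidence of progression in which case the response will be assigned as PD".
- **Date within a visit** (9.4.2.2). When a patient is censored, "the patient will be censored at the latest of the dates contributing to a particular overall visit assessment". This selects a date inside a visit, not which visit.
- **Duration of response** (9.4.2.2). "The end of response should coincide with the date of progression or death from any cause used for the PFS endpoint". The DoR formula also takes over the PFS censoring date.
- **BICR PFS** (9.4.2.2, Sensitivity Analysis). It is analysed in the same way as investigator PFS.
- **Scan schedule** (Table 1). Every 6 weeks "up to 24 weeks relative to randomisation, then Q8W", until objective progression.

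**The concern.** A missed-visit rule exists because, after a long gap, nobody knows when progression happened. The usual answer is to stop follow-up at the last scan that showed the patient progression-free. The printed sentence does this for a patient who dies after the gap without another scan. It does not do it for a patient whose progression is found on the first scan after the gap, because that scan is itself evaluable and is the latest one.

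Such a patient stays in the risk set through a period in which no event could be recorded, and leaves it as censored on the very day progression is documented. Censoring that coincides with the event is informative by construction. It raises the PFS curve, and the DoR curve through the shared date.

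**Working it through.** The protocol shows no PFS event count or power calculation, so there is no figure of its own to reproduce.

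**Step 1. Size of the gap.** Scans fall at Weeks 6, 12, 18, 24, 32, 40, 48 and so on. Credited time = week of PD scan − week of last scan before the gap.

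| Last scan | Missed | PD scan | Censored as printed | Censored before gap | Credited time |
|---|---|---|---|---|---|
| Week 6 | 12, 18 | Week 24 | Week 24 | Week 6 | 18 weeks |
| Week 12 | 18, 24 | Week 32 | Week 32 | Week 12 | 20 weeks |
| Week 18 | 24, 32 | Week 40 | Week 40 | Week 18 | 22 weeks |
| Week 24 | 32, 40 | Week 48 | Week 48 | Week 24 | 24 weeks |

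Both rules censor these patients, so the event count is the same.

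**Step 2. Effect on the curve, by hand.** Assumptions, not in the documents: exponential PFS with median 5 months, and a fraction f of progressions missed on two scans and found on the third. The 6-month estimate is the step at Week 24.

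- Weekly hazard = ln 2 / (5 × 52.18/12) = 0.6931/21.74 = 0.03188.
- True PFS: S(6) = exp(−6 × 0.03188) = 0.8259; S(12) = 0.6821; S(18) = 0.5634; S(24) = 0.4653. Probability of progressing in a 6-week interval: p = 1 − 0.8259 = 0.1741.

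*Censoring before the gap.* Each interval contributes the factor 1 − (1−f)p/(1−fp).
- f = 0.10: 1 − 0.1567/0.9826 = 0.8405; to the fourth power, 0.499.
- f = 0.20: 1 − 0.1393/0.9652 = 0.8557; to the fourth power, 0.536.

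*As printed.* Nobody is censored before Week 18, so KM(18) = 1 − (1−f)(1 − S(18)). At Week 18 the affected patients from the first interval, fp, are censored. Then KM(24) = KM(18) × [1 − (1−f)(S(18) − S(24)) / (KM(18) − fp)].
- f = 0.10: KM(18) = 1 − 0.9 × 0.4366 = 0.6070; KM(24) = 0.6070 × (1 − 0.0883/0.5896) = 0.516.
- f = 0.20: KM(18) = 1 − 0.8 × 0.4366 = 0.6507; KM(24) = 0.6507 × (1 − 0.0785/0.6159) = 0.568.

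The excess is 0.516 − 0.499 = 1.7 points and 0.568 − 0.536 = 3.2 points.

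**Step 3. Simulation of the same setting** (40,000 patients; Monte Carlo error up to √(0.25/40,000) = 0.0025), 6-month PFS:

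| f | As printed | Before gap | PD counted when found | No missed scans |
|---|---|---|---|---|
| 10% | 0.514 | 0.497 | 0.485 | about 0.46 |
| 20% | 0.567 | 0.535 | 0.507 | about 0.46 |

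This agrees with Step 2. The effect of the wording is the first column minus the second. At 48 weeks the printed and before-gap values are 0.27 and 0.25 (10%), and 0.33 and 0.29 (20%).

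**Step 4. A milder missing-visit pattern.** Each visit is missed independently at an assumed rate. The 3- and 6-month medians are the ends of the range that section 2 gives for chemotherapy after an EGFR-TKI. They serve as illustration only.

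| Median | Miss rate | Patients affected | As printed | Before gap | Excess (points) |
|---|---|---|---|---|---|
| 3 months | 5% | 0.6% | 0.287 | 0.285 | 0.2 |
| 3 months | 10% | 2.0% | 0.301 | 0.294 | 0.7 |
| 3 months | 20% | 7.8% | 0.339 | 0.310 | 2.9 |
| 6 months | 5% | 0.6% | 0.533 | 0.532 | 0.1 |
| 6 months | 10% | 2.5% | 0.547 | 0.543 | 0.4 |
| 6 months | 20% | 9.2% | 0.576 | 0.562 | 1.4 |

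**The case against.** **The intent is clear enough.** An evaluable RECIST assessment is not formally defined. Section 9.4.2.1 contrasts progression with the last evaluable assessment when there is none, and the preceding PFS sentence uses nearly the same term for patients without an event. One anchor for progressions and deaths would naturally be the scan before the gap. That is probably what was meant. But the contrast in 9.4.2.1 is made by an explicit qualifier, which the PFS sentence lacks. The preceding sentence uses the term for whatever assessment is last on record. A programmer following the text with the NE/PD split would reach the progression scan.

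**The SAP will settle it.** Section 9.4 says "The SAP will include a more technical and detailed description of the statistical analyses described in this section", and an unseen SAP may name the scan before the gap. That would be reassuring, but this is not a detail left open: the protocol states an operative rule. A SAP that copies it carries the fault into programming, and one that corrects it departs from the protocol.

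**The consequence is small.** This stands. The 10% to 20% scenario is severe. At a 10% per-visit miss rate, 2.0% to 2.5% of patients are affected; even of the 56 once planned, that is 1.1 to 1.4 patients, and recruitment stopped short of 56. PFS is secondary, DoR is descriptive, and section 9.4.1.2 says the study is not meant to support labelling claims.

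**Two stronger inferences fail.** A reader might conclude that the wording causes the event to be lost. It does not: censoring before the gap drops the same event. A reader might also compare the printed rule with about 0.46 and see a 5-point error at 10% affected. That value assumes no scan was missed, which no wording can deliver.

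**Conclusion.** Wrong as written, and minor. For a progression first seen after two or more missed visits, the printed rule gives the progression scan date and credits 18 to 24 unobserved weeks as event-free. For a death with no scan after the gap it gives the right date.

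The excess in 6-month PFS over before-gap censoring is about 2 to 3 points if 10% to 20% of progressions fall after a two-scan gap, and under 1 point at independent per-visit miss rates of 5% to 10%. These sizes rest on exponential PFS and on assumed missingness; the documents give neither. BICR PFS and DoR inherit the rule.

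A reader might infer that the treatment comparison or the primary result is biased. The documents do not support that. ORR does not use the rule, both arms share one scan schedule, and the calculations describe a single arm, so they show nothing about the hazard ratio or the log-rank test.

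**What to change.** In the PFS paragraph of section 9.4.2.2, make three insertions in the sentence that covers missed visits: *immediately* ahead of the count of missed visits, *consecutive* to qualify those visits, and *before the missed visits* after the assessment at which the patient is censored. The first two also stop the rule catching a patient who missed visits early, resumed scanning and progressed later. If no evaluable post-baseline scan precedes the gap, say that the existing Day 1 censoring rule supplies the date.

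State that the same rule governs investigator and BICR PFS and that DoR takes the resulting date, and use identical words in the SAP. An optional sensitivity analysis could count these progressions and deaths as events on their recorded dates.

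The cost is a short wording change. No new data are needed.

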## **6.3 Measures to Minimise Bias: Randomisation and Blinding**

Patient eligibility will be established before treatment randomisation. Once the eligibility of a patient has been confirmed, the investigator (or nominated assistant) should contact the IVRS/IWRS Centralised Randomisation Centre for allocation of randomised therapy.

All patients will be centrally assigned to randomised study intervention using an IVRS/IWRS. Before the study is initiated, the telephone number and call-in directions for the IVRS and/or the log in information and directions for the IWRS will be provided to each site. Patients will be randomised in a 1:1 ratio with stratification according to the number of prior lines of therapy (ie, osimertinib monotherapy as first line or  $\geq$  second line [which includes patients who received osimertinib monotherapy as first line therapy followed by chemotherapy or osimertinib monotherapy after chemotherapy]). If a patient withdraws from the study, then his/her enrolment/randomisation code cannot be re-used. Withdrawn patients will not be replaced.

It is recommended that patients commence study intervention as soon as possible after randomisation, and ideally within 3 days. Patients will complete treatments as specified above or until disease progression is confirmed, unacceptable toxicity occurs, withdrawal of consent, or another discontinuation criterion is met.

The IVRS/IWRS will provide to the investigator(s) or pharmacists the kit identification number to be allocated to the patient at the dispensing visit. Routines for this will be described in the IVRS/IWRS user manual that will be provided to each centre.

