#### **9.4.1.2 Multiplicity Strategy for Primary and Key Secondary Endpoints**

Prior to CSP V3.0, the primary analysis was to occur 6 months after the last patient was randomised. This will be based on a comparison of the primary endpoint (ie, ORR) between treatment groups and will be tested at the 2-sided 5% significance level.

CCI [REDACTED] the secondary efficacy endpoints will be tested at a 2-sided significance level of 5%. There will be no adjustment for multiplicity as the study is not designed to support labelling claims on any of the endpoints.

Final analysis was to be performed after the earlier of 18 months after the last patient was randomised or when 70% of the patients have progressed or died due to any cause. CCI [REDACTED]

Under CSP V3.0, as a result of AstraZeneca's decision to terminate study recruitment early, there will be no primary analysis at the originally planned timepoint. Following early termination of study recruitment, an initial DCO will occur to allow an early review of data by AstraZeneca. A final DCO will occur 9 months after the last patient has been randomised, after which the final analysis will be performed. CCI [REDACTED]

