### **Overall Survival**

Overall survival is defined as the time from randomisation until death due to any cause, regardless of whether the patient withdraws from randomised therapy or receives another anticancer therapy. Any patient not known to have died at the time of analysis will be censored based on the last recorded date on which the patient was known to be alive.

Note: Patients will be contacted for survival follow-up Q12W until death, withdrawal of consent, or the end of the study ie, at the time of final analysis, defined as the earlier of 18 months after the last patient is randomised or when 70% of patients have progressed or died. Patients should be contacted in the week after DCO for each analysis to establish survival status. If patients are confirmed to be alive or if the death date is after the DCO date, these patients will be censored at the date of the DCO.

Overall survival will be analysed as described for the investigator-assessed PFS endpoint (mentioned earlier in this section). CCI

Further details will be provided in the SAP.

Summaries of OS (n, events, medians, quartiles, proportion alive at 3, 6, 9 and 12 months and corresponding 95% CIs) and a Kaplan-Meier plot will be provided.

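### The sparse-strata fallback for PFS changes only the log-rank test, so the p-value would be unstratified while the HR and CI stay on the stratified Cox model

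*Supplement*

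**What the plan says.** The Progression-free Survival text in Section 9.4.2.2 has three parts.

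- **Test:** "Progression-free survival based on investigator assessment will be analysed using a stratified log-rank test adjusting for the same factors as for ORR", which supplies the p-value.
- **Estimate:** "The HR and its CI will be estimated from a stratified Cox Proportional Hazards model", with Efron handling of ties and "the CI calculated using a profile likelihood approach".
- **Fallback:** "If there are insufficient events per strata, a log-rank test will be used to analyse PFS instead of a stratified log-rank test".

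Section 6.3 gives one stratification factor with two levels: "Patients will be randomised in a 1:1 ratio with stratification according to the number of prior lines of therapy", split into osimertinib monotherapy as first line against second line or later.

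The Sensitivity Analysis text in Section 9.4.2.2 analyses BICR-defined PFS in the same way as investigator-assessed PFS. For OS, "Overall survival will be analysed as described for the investigator-assessed PFS endpoint"; redacted text follows that sentence. Section 9.4.1 has results shown with a 95% CI and a p-value unless otherwise stated. Section 9.4.1.2 sets the two-sided 5% level for secondary efficacy endpoints, without multiplicity adjustment because no labelling claim is intended.

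Section 9.4 calls this part of the protocol a summary and leaves the technical detail to a SAP that is to be finalised before unblinding. That SAP is not among the documents.

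**The concern.** A p-value and a confidence interval printed together are read as one analysis. The main PFS analysis meets that expectation, since both test and estimate are stratified. The fallback does not: it withdraws stratification from the test because there are too few events per stratum, yet keeps it in the model that supplies the HR and CI. The two would then rest on different risk sets. One can fall below 0.05 while the other includes 1, and in a small trial they can even point in different directions.

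ORR is treated differently. In Section 9.4.2.1, when responses are too few, the logistic regression itself gives way to a Cochran-Mantel-Haenszel test. The PFS rule changes only half of its analysis.

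What is at stake is the coherence of a reported secondary result. The primary endpoint and its error rate are not affected.

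**Working it through.** **Reading the text.** The sentences run in the order test, estimate, fallback. The fallback names the thing replaced, the stratified log-rank test. No visible sentence moves the Cox model. There is no stated figure to reproduce, so the remaining question is how often the mixed pair would disagree.

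**Formulas.** At event time j, let n be the number at risk, n1 those at risk on the combination, d the events and d1 the events on the combination.

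- Log-rank: U = Σ(d1 − d·n1/n), V = Σ d·(n1/n)(1 − n1/n)(n − d)/(n − 1), and U²/V is referred to chi-square on 1 df. The stratified form builds risk sets within strata and then sums. The unstratified form pools everyone.
- Cox: with treatment the only covariate, the profile-likelihood 95% CI excludes HR = 1 exactly when 2[ℓ(β̂) − ℓ(0)] > 3.84, with ℓ summed over strata in the stratified model.
- Disagreement: exactly one of p < 0.05 and CI excluding 1 holds.

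**Inputs from the protocol.** 1:1 allocation within two strata (6.3); six-weekly scans, which create ties (Table 1); Efron ties and profile-likelihood CI (9.4.2.2); two-sided 5% (9.4.1.2); final data cut-off 9 months after the last randomisation (4.1.4); fewer than the planned 56 patients (9.2).

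**Assumed inputs, because the documents show none.** Final N, stratum sizes, exponential PFS with control median 3 months, treatment HR 0.5 or 1, between-stratum HR 1 to 3.

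**Simulation 1.** 1,500 trials per cell, HR 0.5, follow-up 9 to 24 months. Each cell gives the percentage of trials disagreeing at between-stratum HR 1 / 2 / 3. The last column is the mean event count in the stratum with fewer events.

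| N (strata) | As written: unstratified p, stratified CI | Both unstratified | Fewer-event stratum |
|---|---|---|---|
| 56 (50:50) | 5.8 / 8.9 / 15.7 | 1.7 / 1.9 / 2.3 | about 24-25 |
| 30 (50:50) | 8.1 / 10.7 / 14.8 | 1.9 / 2.6 / 2.6 | about 13 |
| 30 (80:20) | 7.8 / 9.5 / 8.5 | 1.7 / 2.5 / 2.4 | about 5-6 |
| 20 (50:50) | 8.1 / 10.2 / 10.5 | 2.3 / 2.9 / 2.1 | about 8-9 |
| 20 (80:20) | 8.0 / 6.5 / 6.5 | 2.3 / 2.4 / 2.9 | about 4 |

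The Monte Carlo standard error of an 8% rate is √(0.08 × 0.92/1500) = 0.7 percentage points. The largest rates, 14.8% and 15.7%, come from cells whose strata are not sparse, where the fallback would hardly be used. The 80:20 rows bear on it more closely: 6.5-9.5% against 1.7-2.9%. When both are stratified, the pair disagrees in 1.9-5.6% of trials. Across all cells, the log-rank direction and the stratified HR point opposite ways in 0.3-5.1%.

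Under the null (N = 30, between-stratum HR 2), disagreement is 2.7% as written and 0.9% with both unstratified.

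**Simulation 2.** 24 patients, strata of 18 and 6 or 19 and 5, censoring at 6-18 months. At HR 0.5 the mixed pair disagrees in roughly 7-10% of trials, against 2-3% when both are unstratified. At HR 1 it is about 1-3% against about 1%. With continuous event times, so no ties from the scan schedule, matched pairs disagree less: 0.7-1.5% at HR 0.5.

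**How often the fallback would apply.** The protocol gives no number for insufficient events. As an illustration only, fewer than 5 events in either stratum occurs in between almost none and about 58% of the 24-patient trials, depending on the assumptions. Multiplying the upper end by a 7% disagreement rate gives 0.58 × 0.07 = 4.1%. Counted directly, fallback used and pair in disagreement occurs in about 0.2-4% of trials at HR 0.5 and about 1% or fewer at HR 1.

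**The case against.** **The mismatch is read from silence.** The protocol never says that the HR stays stratified, and a reader could take the words about analysing PFS to cover the whole analysis. That is a fair reading of intent. But the sentence states what is replaced, and it is a stratified log-rank test only. If the wider meaning is intended, one clause would say so.

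**The SAP will settle it.** It may. However, the protocol already goes down to tie handling and interval method and attaches no deferral to this rule, so a SAP that follows it faithfully reproduces the mismatch.

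Three stronger readings are tempting, and the documents do not support them.

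- *That the choice between two p-values is left until after unblinding.* Section 9.4 has the SAP finalised before unblinding, so the choice can be fixed there.
- *That the missing numeric trigger is itself a fault.* A threshold of this kind is ordinary SAP detail, and no SAP is shown.
- *That early termination makes the fallback likely.* It makes sparse strata more plausible, but final N and stratum sizes are unknown, and the illustrative trigger ranged from almost never to about 58%.

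Redaction is a further limit. Redacted text follows the final-analysis sentences in Sections 9.4.1.2 and 9.4.2.2 and the OS sentence quoted above. What formal testing remains after early termination, and whether OS follows PFS in every respect, cannot be seen in full.

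It also stands that a stratified Cox HR with sparse strata remains a legitimate estimate. The problem is only its pairing with an unstratified p-value.

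**Conclusion.** The point holds as a wording fault of minor severity (consider). Followed literally, the fallback takes the PFS p-value and the PFS interval from different analyses, and this carries over to BICR PFS and, on the visible text, to OS.

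At HR 0.5 the mixed pair disagrees about the 5% level in roughly 7-10% of simulated 24-patient trials, against 2-3% if both are unstratified; at HR 1 it is about 1-3% against about 1%. These rates rest on assumed N, stratum sizes, control median and effect, and they count only where the fallback is triggered. Matching the models lowers the disagreement but leaves some, because a log-rank p-value is a score test and the interval is a likelihood-ratio one.

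A reader might infer that the PFS conclusion is open to selection or that contradictory results should be expected; neither follows. PFS is a secondary endpoint, and no visible decision turns on its p-value crossing 0.05.

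**What to change.** Add one sentence to the Progression-free Survival text in Section 9.4.2.2, and carry it into the SAP: if events per stratum are insufficient, the log-rank p-value, the HR and its profile-likelihood CI all come from unstratified analyses. Say that the same rule applies to BICR PFS and to OS.

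The numeric trigger can stay with the SAP, provided it is set there before unblinding as Section 9.4 already requires.

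The cost is wording only: no extra data, patients or assessments.
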